### **5.4. Administration**

All AdC68 intramuscular injections are given bilaterally. AdC68 will be administered on Day 1 of Cycles 1 and 2. Please refer to the IP manual for full instructions on the dosage and administration.

pDNA intramuscular injections are given bilaterally. pDNA will be administered beginning on Day 29 of Cycles 1 and 2 and will then be given at 4 week intervals. After Cycle 2, pDNA will continue to be administered every 2 months in the Maintenance Treatment Period. Please refer to the IP manual for full instructions on the dosage and administration of the pDNA and to the TDS-IM Instructions for Use document for the set up and use of the electroporation device. The TDS-IM device should be operated by clinical personnel that have completed the necessary training on device operation.

All IM injections (AdC68 and pDNA) will be given bilaterally in the deltoid muscles or in the vastus lateralis muscles of the quadriceps. Preference should be given to the vastus lateralis muscles when possible.

Tremelimumab will be administered bilaterally subcutaneously at 4 week intervals during Cycles 1 and 2 on the same day as the AdC68 or pDNA dosing beginning with Cohort 3A as described in the **STUDY DESIGN** section. After Cycle 2, tremelimumab will continue to be administered every 2 months in the Maintenance Treatment Period. Both AdC68 or pDNA injections should be given prior to tremelimumab administration. Please refer to the IP manual for full instructions on the dosage and administration of tremelimumab.

Tremelimumab is to be administered in close proximity to the vaccination site. If the vaccination is administered in the vastus lateralis, the tremelimumab is to be administered subcutaneously in either the lower quadrants of the abdomen or the quadriceps. If the vaccination is administered in the deltoid, the tremelimumab is to be administered subcutaneously bilaterally in the outer triceps.

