#### **7.1.7. Cardiac Safety Monitoring**

The algorithm for cardiac Safety Monitoring is shown in [Figure 2](#) below.

For participants undergoing screening, circulating levels of cardiac Troponin-I (cTnI) must be measured and found to be within the normal reference range within 28 days before study entry, preferably using the central laboratory kits provided. Dosing should not proceed until results within the normal reference range have been received by the Investigator. For any results above of the normal reference range (even if borderline), the participant should be referred to a cardiologist by the Investigator for complete cardiac workup and repeat cardiac troponin. The participant can only enter the study after cardiac evaluation, troponin findings within the normal reference range, cardiac clearance and with approval of the Sponsor.

For participants ongoing in the study, circulating levels of cardiac Troponin-I (cTnI) must be measured within 10 days of dosing on the days shown in the [SOA](#) (ie, C1D29, C1D57, C1D85, C2D1, C2D57, month 9 and month 12) and found to be within the normal reference range. No dosing of participants can occur unless the cTnI is within the normal reference range. For any results above the normal reference range (even if borderline) the participant must be referred by the Investigator to a cardiologist for complete work-up and repeat cTnI. Dosing can only occur after cardiac evaluation, cTnI findings within the normal reference range, cardiac clearance and with approval of the Sponsor.

While central laboratory testing for cTnI is preferred, it requires a minimum of 3 days to return results. Therefore, local laboratory testing of cTnI may be used, but only if the timing of measuring cTnI by the central laboratory test (minimum 3 day turnaround time) puts an undue burden or risk on the participant. The use of cardiac troponin-T is strongly discouraged, but could be used in place of cTnI if the central laboratory test puts an undue burden or risk on the participant.

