## Appendix 7. Management of Immune-related Adverse Events (irAEs) including Myasthenia Gravis

Note: References to study treatment in the table below refer to PF-06801591 and/or tremelimumab.

Gastrointestinal irAEs		
Severity of Diarrhea/Colitis (NCI-CTCAE v4)	Initial Management	Follow-up Management
Grade 1 Diarrhea: <4 stools/day over Baseline.  Colitis: asymptomatic.	-Continue study treatment.  -Symptomatic treatment (eg, loperamide).	-Close monitoring for worsening symptoms.  -Educate patient to report worsening immediately.  -If worsens: Treat as Grade 2, 3 or 4.
Grade 2 Diarrhea: 4 to 6 stools per day over Baseline; IV fluids indicated <24 hours; not interfering with ADL.  Colitis: abdominal pain; blood in stool.	-Withhold study treatment. -Symptomatic treatment.	-If improves to Grade $\leq 1$ : Resume study treatment.  -If persists >5-7 days or recurs: Treat as Grade 3 or 4.
Grade 3 to 4 Diarrhea (Grade 3): $\geq 7$ stools per day over Baseline; incontinence; IV fluids $\geq 24$ h; interfering with ADL.  Colitis (Grade 3): severe abdominal pain, medical intervention indicated, peritoneal signs.  Grade 4: life-threatening, perforation.	-Withhold for Grade 3. -Permanently discontinue study treatment for Grade 4 or recurrent Grade 3.  -1.0 to 2.0 mg/kg/day prednisone IV or equivalent.  -Add prophylactic antibiotics for opportunistic infections.  -Consider lower endoscopy.	-If improves: -Continue steroids until Grade $\leq 1$ , then taper over at least 1 month; resume study treatment following steroids taper (for initial Grade 3).  -If worsens, persists >3 to 5 days, or recurs after improvement: -Add infliximab 5 mg/kg (if no contraindication).  -Note: infliximab should not be used in cases of perforation or sepsis.

Dermatological irAEs		
Grade of Rash (NCI-CTCAE v4)	Initial Management	Follow-up Management

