New onset of cardiac signs or symptoms and/or new laboratory cardiac biomarker elevations (eg, troponin, CK-MB, BNP) or cardiac imaging abnormalities suggestive of myocarditis.	
 
-Withhold study treatment.
 
-Hospitalize.
 
-In the presence of life threatening cardiac decompensation, consider transfer to a facility experienced in advanced heart failure and arrhythmia management.
 
-Consult cardiologist to establish etiology and rule-out immune-mediated myocarditis.
 
-Guideline based supportive treatment as per cardiology consult.*
 
-Consider myocardial biopsy if recommended per cardiology consult.
 
	
 
-If symptoms improve and immune-mediated etiology is ruled out, re-start study treatment.
 
-If symptoms do not improve/worsen, viral myocarditis is excluded, and immune-mediated etiology is suspected or confirmed following cardiology consult, manage as immune-mediated myocarditis.
 

Immune-mediated myocarditis.	
 
-Permanently discontinue study treatment.
 
-Guideline based supportive treatment as appropriate as per cardiology consult.* 1.0 to 2.0 mg/kg/day prednisone or equivalent.
 
-Add prophylactic antibiotics for opportunistic infections.
 
	
 
-Once improving, taper steroids over at least 1 month.
 
If no improvement or worsening, consider additional immunosuppressants (eg, azathioprine, cyclosporine A).
 

\*Local guidelines, or eg, ESC or AHA guidelines

ESC guidelines website: <https://www.escardio.org/Guidelines/Clinical-Practice-Guidelines> AHA guidelines website:

<http://professional.heart.org/professional/GuidelinesStatements/searchresults.jsp?q=&y=&t=1001>

Endocrine irAEs		
Endocrine Disorder	Initial Management	Follow-up Management

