### Recommended Management Algorithm for Myasthenia Gravis

**Suspicion or Early Diagnosis of Myasthenia Gravis**  
**Timing, education of the patient, awareness of the physician are essential**

**Early identification and individually determined treatment of patients who develop MG after receiving checkpoint inhibitors is critical.**

Once identified, or a suspicion is raised, patients should be seen by a neuromuscular specialist expert in diagnosing and treating MG. Treatment with all components of PrCa VBIR and PF-06801591 (if applicable) must be discontinued while evaluate of MG is in progress. Treatment with all components of PrCa VBIR and PF-06801591 (if applicable) must be permanently discontinued if a clinical diagnosis of MG is made.

Treatment of MG must be individualized based on individual factors, and should be determined for each diagnosed patient by this expert.

Depending on the algorithm-based supportive care, a primary treatment may be started if timely consultation with an expert was not possible.

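### The Appendix 7 suspected-myocarditis row is weaker than Section 7.1.7, and for lower-grade suspicion without a raised cTnI no visible text expressly holds pDNA or sets a cTnI or Sponsor condition for restart

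*Protocol*

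**What the plan says.** The first row of the Appendix 7 cardiac table has broad triggers: "New onset of cardiac signs or symptoms and/or new laboratory cardiac biomarker elevations (eg, troponin, CK-MB, BNP) or cardiac imaging abnormalities suggestive of myocarditis". Its initial management is to withhold study treatment, hospitalize and consult a cardiologist. Its restart line is "If symptoms improve and immune-mediated etiology is ruled out, re-start study treatment". The note at the head of the appendix limits the term: "References to study treatment in the table below refer to PF-06801591 and/or tremelimumab". pDNA and AdC68 are therefore outside the instruction to withhold.

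Section 7.1.7 lists seven on-study cTnI days, "C1D29, C1D57, C1D85, C2D1, C2D57, month 9 and month 12", and then states "No dosing of participants can occur unless the cTnI is within the normal reference range". After any result above range, even a borderline one, it requires referral to a cardiologist and adds "Dosing can only occur after cardiac evaluation, cTnI findings within the normal reference range, cardiac clearance and with approval of the Sponsor". These sentences speak of dosing in general, not of the antibodies alone.

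The myasthenia gravis algorithm in the same appendix uses wider wording: "Treatment with all components of PrCa VBIR and PF-06801591 (if applicable) must be discontinued while evaluate of MG is in progress".

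**The concern.** Two rules for the same clinical event differ in which products they stop and in what they require before restart. A site that follows the Appendix 7 row literally, even when the trigger is a raised troponin, gets a less protective instruction than Section 7.1.7. It is also less protective than the rule the same appendix applies to suspected myasthenia gravis.

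The row has triggers other than troponin. If the suspicion comes from symptoms, CK-MB, BNP or imaging, the Section 7.1.7 conditions may never be triggered. At stake is a vaccine dose given, or antibodies restarted, while the cardiac question is not fully closed. This matters because Amendment 8 added troponin testing precisely to reduce the risk from myocarditis. It is a participant-safety point and has no bearing on the SAP.

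**Working it through.** There is no stated figure to reproduce. The check is a comparison of rules, followed by a count of visits.

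**Which rule holds pDNA, and what restart needs**

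| Situation | pDNA held during work-up? | Condition for restart |
|---|---|---|
| cTnI above range | Yes, Section 7.1.7 bars dosing | Evaluation, in-range cTnI, cardiac clearance, Sponsor approval (7.1.7); the Appendix 7 row asks for less |
| Potentially related Grade 3–4 or intolerable Grade 2 | Yes, Section 5.4.2 interrupts all components, at any visit | Recovery criteria in 5.4.2; Sponsor agreement if the interruption exceeds 2 weeks |
| Myocarditis confirmed, any grade | Permanent discontinuation (Table 6 footnote) | None |
| Grade 1 or tolerable Grade 2 suspicion from symptoms, CK-MB, BNP or imaging, with cTnI in range or unmeasured | No express hold in the visible text | The row only: symptoms improved and immune cause excluded. Sponsor input arises only after 2 weeks (5.4.2, related) or 4 weeks (5.4.3, unrelated) |

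In the first two situations the row conflicts with a stronger rule elsewhere. Only the last is a gap.

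**How often a vaccine dose falls on a day with no scheduled cTnI (Cohorts 3B and 5B)**

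The inputs are the study-treatment schedule for 3B and 5B, the maintenance schedule for those cohorts, and the cTnI days in Section 7.1.7.

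- pDNA visits in Cycles 1–2: Days 29, 57 and 85 of each cycle = 6.
- pDNA visits in maintenance to month 22: months 10, 12, 14, 16, 18, 20, 22 = 7.
- Total: 6 + 7 = 13.
- With a scheduled cTnI: C1D29, C1D57, C1D85, C2D57, month 12 = 5. The other two cTnI days carry no pDNA: C2D1 is an AdC68 day, and month 9 is PF-06801591 only.
- Without a scheduled cTnI: 13 − 5 = 8, and 8/13 = 62%. These are C2D29, C2D85 and months 10, 14, 16, 18, 20, 22, that is 2 of 6 in Cycles 1–2 and 6 of 7 in maintenance.

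For AdC68, "AdC68 will be administered on Day 1 of Cycles 1 and 2". After C1D1 its only dose is at C2D1, a scheduled cTnI day, so 0 of 1 later AdC68 doses can fall due with cTnI unscheduled. The unmeasured-cTnI case therefore concerns pDNA alone among the vaccine components.

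**Whether closed enrollment makes this moot**

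- Section 1.3.2 lists enrollment at 11 November 2019 by cohort: 7 + 6 + 20 + 7 + 12 + 3 + 14 = 69. None is in 3B.
- From 11 November 2019 to Amendment 8 on 29 May 2020 is 200 days, so no 3B participant was past study day 200.
- C2D85 is study day 113 + 84 = 197, and month 10 is 197 + 56 = 253.

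Any 3B participant who receives maintenance pDNA therefore does so after Amendment 8. The documents do not say how many reach that point.

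**The case against.** The case on the other side is substantial.

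- **The scenario is remote.** The participant is in hospital under a cardiologist. Hospitalization is ordinarily an SAE notified to the sponsor within 24 hours (Sections 8.6 and 8.14.1). Section 5.4.1 lets dosing be delayed for significant toxicity. Section 14 pauses study dosing for serious Grade 4 or 5 cardiac events of special interest. An investigator is unlikely to electroporate during the work-up. This stands and keeps the point small. SAE notice, however, informs the Sponsor and does not make restart depend on its approval, and the Section 14 grades lie outside the residual case.
- **Section 7.1.7 may already cover every dose.** Read alone, its sentence barring dosing without an in-range cTnI has no exception. But it follows a list of scheduled days, and a site can reasonably confine it to them.
- **Figure 2, the cardiac algorithm, could not be seen.** It may contain a wider rule. This stands, so the gap can be asserted only for the visible text.
- **The antibody-only definition governs the whole appendix table.** On this view the myasthenia gravis rule is a special case, added after an event in this study. That is fair as history. It does not explain why the cardiac row asks less than the protocol's own cardiac section.

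Two stronger readings are tempting and are not supported. First, a reader might infer that pDNA is unprotected at all eight uncovered visits whenever myocarditis is suspected. Sections 5.4.2 and 7.1.7 rule that out for the higher grades and for a raised cTnI. Second, a reader might cite Section 5.4.4.3 as showing that the vaccine continues while the antibodies are held. That section concerns resuming PrCa VBIR, which includes tremelimumab, without PF-06801591 after an interruption. It does not describe pDNA given while tremelimumab is held. In these cohorts pDNA is scheduled together with tremelimumab, and no visible text provides for pDNA alone.

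**Conclusion.** The inconsistency is plain on the page: the Appendix 7 row withholds fewer products and sets a lower bar for restart than Section 7.1.7, even when troponin is the trigger. The uncovered case is limited to suspicion at Grade 1 or tolerable Grade 2, without an above-range cTnI, and with restart falling inside the 2-week or 4-week limits. For that case the visible text neither expressly holds pDNA nor requires a cTnI or Sponsor approval.

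The figure of 8 of 13 pDNA visits (62%) shows where a dose can come due with no scheduled cTnI. It is not an estimate of risk, and its end at month 22 is simply the last month the schedule names, since dosing may continue. No participant count can be given.

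The conclusion assumes that study treatment means what the Appendix 7 note says, that the Section 7.1.7 bar is tied to its listed days, and that Figure 2 holds no broader rule. On those terms this is a minor safety harmonization that is cheap and worth making.

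**What to change.** Change two lines in the first row of the Appendix 7 cardiac table.

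1. Initial management: *Withhold all components of PrCa VBIR and PF-06801591 while myocarditis is evaluated.*
2. Restart: *Re-start only if symptoms have improved, an immune-mediated cause has been excluded, and the Section 7.1.7 conditions are met (cardiac evaluation, in-range cTnI, cardiac clearance, Sponsor approval).* This should apply whatever the trigger, and whether or not a cTnI is scheduled that day.

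If Figure 2 already says this, the row should refer to it.

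The cost per suspected case is one unscheduled cTnI, which is a test already in the protocol, one Sponsor sign-off, and possibly a delayed vaccine dose.

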### Recommended Management Algorithm for Myasthenia Gravis

**Suspicion or Early Diagnosis of Myasthenia Gravis**  
**Timing, education of the patient, awareness of the physician are essential**

**Early identification and individually determined treatment of patients who develop MG after receiving checkpoint inhibitors is critical.**

Once identified, or a suspicion is raised, patients should be seen by a neuromuscular specialist expert in diagnosing and treating MG. Treatment with all components of PrCa VBIR and PF-06801591 (if applicable) must be discontinued while evaluate of MG is in progress. Treatment with all components of PrCa VBIR and PF-06801591 (if applicable) must be permanently discontinued if a clinical diagnosis of MG is made.

Treatment of MG must be individualized based on individual factors, and should be determined for each diagnosed patient by this expert.

Depending on the algorithm-based supportive care, a primary treatment may be started if timely consultation with an expert was not possible.

1. AMENDMENTS FROM PREVIOUS VERSION(S)

Amendment 2	Section 2.1	Study design texts are updated to be consistent with the protocol amendment. A new study design schema replaces the previous one.
	Section 2.2	Objectives are described separately for Part A and Part B.
	Section 4.3	Sample size languages are updated according to the protocol amendment.
	Section 6	Endpoints are described separately for Part A and Part B.
	Section 8.1.3	Efficacy analyses languages are updated to provide more clarity.
	Section 8.1.4	A PSA-50 response rate analysis is added.
	Section 8.1.5.2	Sunitinib PK section is deleted according to the protocol amendment.
	Section 10.3	A censoring rule is added for COVID-19 caused missing tumor assessments.
Amendment 1	Section 2.1	Editorial updates to match the protocol
	Section 4.3	Added from the protocol
	Section 5.3	The definition for the per-protocol population is updated to match the protocol.
	Section 6	Texts about endpoints are updated to match the protocol
	Section 8.1.2.1	Texts added to define “treatment related AE”
	Section 8.1.3	Details added about tumor response analyses and time to event analyses.
	Section 8.1.5.3	A section about PF-06801591 PK analysis is added to match the protocol
	Section 10.3	Time to event censoring rules added

2. INTRODUCTION

This document presents the statistical analysis plan (SAP) for study B7791001. The SAP is based on the protocol amendment 7 dated November 22, 2019 and protocol amendment 8 dated May 29, 2020.

Note: in this document any text taken directly from the protocol is *italicized*.

[figure not shown]
2.1. Study Design

This is a Phase 1, open label, multi-center, multiple dose, safety, PK, PD and immunogenicity study evaluating the components of a vaccine-based immunotherapy regimen for prostate cancer (PrCa VBIR). PrCa VBIR consists of the following components: Adenovirus (AdC68), pDNA and tremelimumab. In addition, cohorts will evaluate PrCa VBIR when given in combination with PF-06801591.

The study will enroll patients with the following stages of prostate cancer: patients with asymptomatic/minimally symptomatic metastatic castration-resistant prostate cancer (mCPRC) who have not received secondary hormones (M1 pre-secondary hormones), patients with rising PSA at high risk for recurrence (biochemically relapsed), and asymptomatic/minimally symptomatic mCPRC patients for whom secondary hormone treatment failed (M1 post-secondary hormones). The study is divided in to two parts, Dose Escalation (Part A) followed by Dose Expansion (Part B).

The overall study design is presented in Figure 1.

Figure 1. Overall Study Design

2.2. Study Objectives

Part A Primary Objective

- *To assess safety and tolerability of increasing dose levels of the prostate cancer vaccine-based immunotherapy regimen (PrCa VBIR) components alone and in combination with increasing doses of PF-06801591.*
- *To characterize the dose limiting toxicities (DLTs), if any are observed, and overall safety profile of escalated doses of the PrCa VBIR components alone and in combination with increasing doses of PF-06801591.*
- *To determine the Part B Expansion Dose for the PrCa VBIR components, and in combination with PF-06801591.*

Part A Secondary Objectives

- *To evaluate the immune response elicited by the PrCa VBIR to the selected prostate cancer tumor-antigens.*
- *To evaluate the overall safety profile in prostate cancer participants.*
- *To evaluate the PK of tremelimumab after subcutaneous(SC) administration.*
- *To evaluate the PK of PF-06801591 after SC administration*
- *To evaluate the anti-drug antibody (ADA) response of tremelimumab after SC administration with the other PrCa VBIR components.*
- *To evaluate the ADA response of PF-06801591 after SC administration with the other PrCa VBIR components.*

Part A Exploratory Objectives

- *To document any preliminary evidence of anti-tumor activity.*

REDACTED

REDACTED

Part B Primary Objective

- *To evaluate the overall safety profile of the PrCa VBIR + PF-06801591 in prostate cancer participants.*

Part B Secondary Objectives

- *For Cohort 3B: To evaluate the anti-tumor response induced by treatment in participants with mCRPC utilizing solid tumor response criteria.*
- *For Cohort 3B: To evaluate the anti-tumor response induced by treatment utilizing immune related response criteria.*
- *For Cohort 3B: to evaluate bone metastatic disease outcome in participants with mCRPC.*
- *For Cohorts 3B: To estimate the duration of radiographic Progression-Free Survival (rPFS) in participants with mCRPC.*
- *To evaluate response rate based on 50% reduction of prostate specific antigen (PSA).*
- *To evaluate PSA kinetics.*
- *To evaluate trough concentrations of tremelimumab after SC administration at selected doses.*
- *To evaluate trough concentrations of PF-06801591 after SC administration at selected doses.*
- *To evaluate the anti-drug antibody (ADA) response of tremelimumab after SC administration with the other PrCa VBIR components.*
- *To evaluate the ADA response of PF-06801591 after SC administration with the other PrCa VBIR components.*

CCI [REDACTED]

3. INTERIM ANALYSES, FINAL ANALYSES AND UNBLINDING

There are no formal interim analyses planned in this study. However, this is an open label study, and therefore, the Pfizer team will review safety, immunogenicity, pharmacokinetics, pharmacodynamic, CCI [REDACTED] and other data throughout the study.

